6.5.3 Other concomitant treatment

Other medication other than that described above, which is considered necessary for the subject's safety and wellbeing, may be given at the discretion of the investigator and recorded in the appropriate sections of the eCRF.

6.6 Dose delay and modification

6.6.1 Acalabrutinib

The actions in [Table 8](#) should be taken for the following toxicities (according to CTCAE criteria version 5.0):

- Grade 4 neutropenia (ANC <500/ μ L) for >7 days (myeloid growth factors are permitted per Consensus of Chinese Experts [Version 2015] and use must be recorded on the eCRF)
- Grade 3 platelets decreased in the presence of clinically significant bleeding
- Grade 4 platelets decreased
- Grade 3 or 4 nausea, vomiting, or diarrhea, if persistent despite optimal antiemetic and/or anti-diarrheal therapy
- Any other Grade 4 toxicity or unmanageable Grade 3 toxicity

If the toxicity resolves or reverts to CTCAE Grade 1 or baseline within 28 days of onset and the subject is showing clinical benefit, treatment with acalabrutinib may be restarted using the rules below for dose modifications (see [Table 8](#)). Whenever possible, any dose adjustment of acalabrutinib should be discussed between the investigator and the sponsor before implementation. The appropriate clinic staff should dispense the study drug for the new dose level and instruct the subject/caregiver about the change in dose level. Any changes to the dosing regimen must be recorded in the appropriate eCRF.

Once de-escalation has occurred, the dose should not restart at original dose level.

Treatment with acalabrutinib should be held for any unmanageable, potentially study drug-related toxicity that is Grade ≥ 3 in severity. Any other clinically important events where dose delays may be considered appropriate by the investigator must be discussed with the sponsor.

Study drug may be held for a maximum of 28 consecutive days from expected dose. Study treatment should be discontinued in the event of a toxicity requiring the postponement of dosing lasting >28 days, unless reviewed and approved by the sponsor.

Note: Temporary withholding of study drug for as little as 7 days can cause a transient worsening of disease and/or of constitutional symptoms. Refer to [Section 7.1](#) for more information on assessing disease progression under these circumstances.

Table 8 Acalabrutinib Dose Modification

Occurrence	Action
1st-2 nd	Hold acalabrutinib until recovery to Grade 1 or baseline; may restart at original dose level (100 mg BID)
3 rd	Hold acalabrutinib until recovery to Grade 1 or baseline; restart at one dose level lower (100 mg QD)
4th	Discontinue acalabrutinib.
Abbreviations: BID=twice daily; QD=once per day.	

6.6.2 Rituximab and chlorambucil

If a patient experiences any \geq Grade 2 non-hematological toxicity, chlorambucil and/or rituximab should be hold until the non-hematological toxicity returns to Grade 1 or baseline. If treatment is delayed for more than 4 weeks due to study drug-related toxicity, chlorambucil and/or rituximab should be discontinued.

If a patient experiences Grade 3 or 4 cytopenia, the guidelines for dose delay (chlorambucil or rituximab) and dose reduction (chlorambucil only) are outlined in [Table 9](#).

Table 9 Rituximab and Chlorambucil Dose Modification

	Chlorambucil	Rituximab
Grade 3 or 4 cytopenia	Delay dosing for a maximum of 4 weeks. Administer G-CSF for neutropenia or platelets or red blood cells as required. 1st episode : If improvement to Grade ≤ 2 (or baseline), decrease Clb dose to 75% of initial dose for subsequent cycles 2nd episode : If improvement to Grade ≤ 2 (or baseline), decrease Clb dose to 50% of initial dose for subsequent cycles 3rd episode : Discontinue Clb	If improvement to Grade ≤ 2 (or baseline), administer full dose. If Clb is discontinued, rituximab may continue at the investigator's discretion.
Grade 1 or 2 cytopenia	No dose reduction or delay	No dose reduction or delay
Abbreviations: Clb=chlorambucil; G-CSF=granulocyte colony-stimulating factor.		

No reduction in the dose of rituximab is allowed. Severe, including fatal, infusion reactions can occur with rituximab. Discontinue rituximab infusion and provide medical treatment for Grade 3 or 4 infusion reactions. For less severe infusion reactions (grade 1 or 2), interrupt the infusion or slow the infusion rate. Rituximab may continue at the discretion of the investigator when the toxicity has improved (Grade ≤ 2 for hematological toxicity and Grade 1 or baseline for non-hematological toxicity). If rituximab is discontinued, the patient is

withdrawn from study treatment. Refer to the rituximab local prescribing information for dose withholding or discontinuation in response to specific toxicities associated with rituximab.

Chlorambucil dose reductions are described in Table 9. Once reduced, the dose of chlorambucil should not be escalated. A delay of up to 4 weeks is permitted for chlorambucil to allow recovery of hematologic toxicities to Grade ≤ 2 or non-hematologic toxicities to Grade 1 or baseline level. If the treatment is delayed for more than 4 weeks due to toxicity, chlorambucil should be discontinued.

If a Grade 3 or 4 cytopenia prevents treatment on Day 15 (of any cycle for Arm B), the Day 15 chlorambucil dose will be skipped in order to keep the antibody on schedule. Rituximab + chlorambucil administration on Day 1 of the following cycle will be given if the cytopenia has resolved to Grade ≤ 2 . Chlorambucil will be given at a reduced dose. If the cytopenia persists, rituximab + chlorambucil administration will be delayed until the cytopenia has improved to Grade ≤ 2 .

Chlorambucil has been reported to exacerbate or precipitate autoimmune hemolytic anemia and patients should be monitored carefully for this condition. If a rapid decrease of hemoglobin occurs during therapy, the possibility of chlorambucil- or autoantibody-induced hemolysis should be considered and appropriate diagnostic tests (LDH, bilirubin, haptoglobin, reticulocytes, Coombs test) should be performed. If hemolysis is suspected, a Coombs test should be performed. If, in the judgment of the treating physician, there is evidence of clinically significant hemolytic anemia secondary to chlorambucil, study treatment should be promptly withdrawn. Full details of the hemolytic anemia should be recorded on the adverse event pages of the eCRF.

As many of these patients have multiple comorbidities, treatment may be delayed longer than 4 weeks (for both treatments) to enable resolution of unrelated AEs, concurrent diseases, or recovery from surgical procedures. This is at the investigators discretion but should be discussed in advance with the sponsor.

A patient should discontinue study treatment with chlorambucil/rituximab if any of the following occur:

- Grade 4 infusion related symptom (patient should be withdrawn immediately)
- Grade 3 infusion related symptom at re-challenge
- Grade 3 or 4 cytopenia that has not resolved to Grade ≤ 2 and delays treatment by 4 weeks
- Grade ≥ 2 non-cytopenic toxicity that does not resolve to Grade 1/baseline and delays treatment by 4 weeks

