 - (d) Progressive lymphocytosis with an increase of >50% over a 2-month period or a lymphocyte doubling time (LDT) of <6 months. LDT may be obtained by linear regression extrapolation of absolute lymphocyte count (ALC) obtained at intervals of 2 weeks over an observation period of 2 to 3 months. In subjects with initial blood lymphocyte counts of $30 \times 10^9/L$ (30,000/ μ L), LDT should not be used as a single parameter to define indication for treatment. In addition, factors contributing to lymphocytosis or lymphadenopathy other than CLL (e.g., infections) should be excluded.
 - (e) Autoimmune anemia and/or thrombocytopenia that is poorly responsive to standard therapy
 - (f) Symptomatic or functional extranodal involvement (e.g., skin, kidney, lung, spine).

- (g) B-symptoms documented in the subject's chart with supportive objective measures, as appropriate, defined as ≥ 1 of the following disease-related symptoms or signs:
 - (i) Unintentional weight loss $\geq 10\%$ within the previous 6 months before Screening
 - (ii) Significant fatigue (ECOG performance status 2 or higher; inability to work or perform usual activities)
 - (iii) Fevers higher than 100.5°F or 38.0°C for ≥ 2 weeks before Screening without evidence of infection
 - (iv) Night sweats for ≥ 1 month before Screening without evidence of infection
- 7 Meet the following laboratory parameters:
 - (a) Adequate bone marrow function independent of growth factor or transfusion support 1 week before assessment, as follows:
 - (i) Absolute neutrophil count (ANC) ≥ 750 cells/ μL ($0.75 \times 10^9/\text{L}$); ANC ≥ 500 cells/ μL ($0.50 \times 10^9/\text{L}$) in subjects with documented bone marrow involvement of CLL
 - (ii) Platelet count $\geq 50,000$ cells/ μL ($50 \times 10^9/\text{L}$); platelet count $\geq 30,000$ cells/ μL ($30 \times 10^9/\text{L}$) in subjects with documented bone marrow involvement of CLL
 - (b) Serum aspartate aminotransferase (AST) and alanine aminotransferase (ALT) $\leq 2.5 \times$ upper limit of normal (ULN)
 - (c) Total bilirubin $\leq 2.0 \times$ ULN, unless directly attributable to Gilbert's syndrome
 - (d) Estimated creatinine clearance of ≥ 30 mL/min using the Cockcroft-Gault equation (Appendix E)

Reproduction

- 8 Negative pregnancy test (urine or serum) for female subjects of childbearing potential prior to enrollment
- 9 Prior to the planned date of randomization for female subjects, at least 1 of the following criteria should be met:

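### Section 6.6.2 sets two different recovery thresholds for Arm B cytopenia, and they conflict for eligible patients who enter at Grade 3

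*Protocol*

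**What the plan says.** All the rules at issue are in Protocol Section 6.6.2.

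- **Table 9.** For a Grade 3 or 4 cytopenia, dosing may resume on improvement to Grade 2 or lower, or to baseline. The rituximab column ends "or baseline), administer full dose". The chlorambucil column, first episode, reads "or baseline), decrease Clb dose to 75% of initial dose for subsequent cycles"; a second episode takes chlorambucil to 50% and a third stops it. The rituximab column adds "If Clb is discontinued, rituximab may continue at the" investigator's discretion.
- **Text below Table 9.** Rituximab may continue once toxicity has improved to Grade 2 or lower "for hematological toxicity and Grade 1 or baseline for non-hematological toxicity". The sentence on the permitted chlorambucil delay makes the same split.
- **Next-cycle Day 1 rule.** If a cytopenia persists, giving the two drugs "administration will be delayed until the cytopenia has improved to Grade" 2 or lower.
- **Stop list.** It opens "A patient should discontinue study treatment with chlorambucil/rituximab if any of the following occur". The cytopenia item is "Grade 3 or 4 cytopenia that has not resolved to Grade" 2 or lower and that delays treatment by 4 weeks. The next item, on non-cytopenic toxicity, does accept return to baseline.

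Inclusion criterion 7 (Section 5.1) requires an ANC of at least 750/µL and platelets of at least 50,000/µL. The floors drop to 500/µL and 30,000/µL "in subjects with documented bone marrow involvement of CLL". It lists no hemoglobin floor.

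**The concern.** For a patient whose counts were better than Grade 3 at entry, the two thresholds seldom differ in practice. For a patient who enters at Grade 3 they conflict: unchanged counts satisfy the baseline alternative at once and never satisfy Grade 2 or lower. Two sites could treat identical control patients differently, each following the protocol.

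The conflict is confined to the control arm, because Section 6.6.1 and Table 8 accept recovery to Grade 1 or baseline for acalabrutinib. What is at stake is how much control treatment such patients receive and how Arm B exposure and discontinuations can be interpreted. It also touches deviation coding. SAP Section 2.2 counts as important a patient who met a treatment-stopping criterion but was not withdrawn, and whether that criterion was met depends on which sentence governs.

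**Working it through.** **1. Thresholds side by side.**

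| Place in Section 6.6.2 | Cytopenia must reach |
|---|---|
| Table 9, both drugs | Grade 2 or lower, or baseline |
| Text below Table 9, rituximab | Grade 2 or lower |
| Text below Table 9, chlorambucil delay | Grade 2 or lower |
| Next-cycle Day 1 rule | Grade 2 or lower |
| Stop list | Grade 2 or lower |

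The missing baseline wording is not shorthand. The two sentences below the table and the stop list each attach baseline to non-hematological toxicity and leave it off cytopenia.

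**2. Can an eligible patient enter at Grade 3?** Section 6.6.1 gives Grade 4 neutropenia as ANC below 500/µL. Criterion 7 admits ANC of 500/µL with marrow involvement. That patient is just above Grade 4, so Grade 3. This follows from the documents. The upper Grade 3 limit for ANC and the platelet limits are not printed. If Grade 3 is assumed to be ANC 500–999/µL and platelets 25,000–49,999/µL, both ANC floors and the lower platelet floor fall within it.

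**3. Dose consequences for unchanged Grade 3 counts.** Planned chlorambucil (Table 6): 12 × 0.5 = 6.0 mg/kg. Planned rituximab: 375 + 5 × 500 = 2875 mg/m² over 6 infusions.

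*Text rules, read literally.* Cycle 1 Day 1 is given and Day 15 is skipped. Cycle 2 Day 1 (day 29) is delayed 28 days to day 57, and then treatment stops.
- Chlorambucil: 0.5/6.0 = 8.3% (1 of 12 doses)
- Rituximab: 375/2875 = 13.0% of planned mg/m² (1 of 6 infusions)

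*Table 9.* Rituximab is 6 of 6. Chlorambucil depends on how episodes are counted:
- One continuing episode, 75% from Cycle 2: (2 × 0.5 + 10 × 0.375)/6.0 = 79.2%. With Cycle 1 Day 15 skipped: (0.5 + 3.75)/6.0 = 70.8%.
- A new episode each cycle (75%, 50%, stop): (1.0 + 0.75 + 0.5)/6.0 = 37.5%. With Cycle 1 Day 15 skipped: (0.5 + 0.75 + 0.5)/6.0 = 29.2%.

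The range is therefore about 29–79%, with no Day 15 dose after Cycle 1 skipped.

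**4. Which drug stops, and when.**
- Opening paragraph: chlorambucil, rituximab or both, after more than 4 weeks for study drug-related toxicity. The paragraph begins with non-hematological toxicity.
- Text below Table 9: chlorambucil, after more than 4 weeks.
- Table 9: rituximab may go on when chlorambucil stops.
- Stop list: the two names joined by a slash, when treatment is delayed by 4 weeks.

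Section 6.6.2 also says that stopping rituximab means withdrawal from study treatment, so the answer decides whether the patient stays on treatment at all.

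**5. Timing.** Arm B treatment lasts at most 6 × 28 = 168 days. The final analysis required completed enrollment (Section 9.2). It has been done (Synopsis), about 45 months after first randomization (Section 4.4), against a planned accrual of about 30 months.

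**The case against.** The strongest reply is that the section gives investigators enough room to avoid the extreme outcome. Table 9 provides for growth factor, platelets or red cells during a delay. A delay beyond 4 weeks is allowed for unrelated events or concurrent disease, after discussion with the sponsor, and a marrow-related baseline cytopenia might qualify. The one-treatment-day result also requires that the same count permits Cycle 1 Day 1, prevents Day 15 and stays at Grade 3 throughout. All of this stands. It makes the extreme outcome possible rather than routine, but none of it says which threshold governs.

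A reader might infer that Table 9 lets such a patient be dosed as planned. It does not: return to baseline still brings the chlorambucil reductions. Full dosing arises only if a stable entry count is not counted as a cytopenia the patient experiences, and the protocol does not say so.

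A reader might also see a clean contradiction over which drug stops. That is only partly so. Rituximab's continuation is itself conditional on improvement, and the Table 9 remark about continuing without chlorambucil can be read as covering the third-episode stop. The slash can mean the regimen or either drug. What remains is ambiguity, plus a small mismatch in the 4-week trigger.

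Finally, the Day 15 skip sentence should not be counted among the stricter thresholds. It applies when a cytopenia prevents treatment and states no recovery level.

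**Conclusion.** The threshold conflict is real: one section gives opposite instructions for the same eligible patient. With unchanged Grade 3 counts, the range runs from full rituximab with about 29–79% of planned chlorambucil to 8.3% of chlorambucil and 13.0% of rituximab. The lower end assumes a literal reading and no use of supportive measures or the longer-delay clause. That an ANC at the criterion 7 floor is Grade 3 rests on the protocol's own Grade 4 limit and a scale without gaps; other grade limits are assumed.

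A reader might go on to infer that the control arm was weakened and the PFS hazard ratio shifted towards acalabrutinib. The documents do not support a statement of that kind. They give neither the share of patients entering at Grade 3 nor the rule sites followed, so neither the number affected nor any effect on the hazard ratio can be computed.

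Unless accrual ran well beyond plan, Arm B dosing had ended before this version of the protocol. The point now matters mainly for interpreting Arm B exposure, discontinuations and deviations. It should be corrected, but it is not a must-fix item.

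**What to change.** Reconcile Table 9 with the text of Section 6.6.2 so that the delay, resume and stop rules share one recovery threshold, checked against the counts criterion 7 allows at entry. State once whether a cytopenia unresolved at 4 weeks ends chlorambucil only, either drug or both, and use one form of the 4-week trigger. The sponsor's medical team should choose the version; this review takes no position on it.

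Because the final analysis is done, the clinical study report should also state which rule sites applied, alongside the Arm B exposure, dose delay and discontinuation summaries in SAP Sections 4.2.6.1 and 4.2.6.2. Giving the number of Arm B patients who entered at Grade 3 would show how far the conflict could have reached.

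The cost is wording in one section and a short statement in the report. No added patients, visits or tests are needed.

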6.7 Treatment after the end of the study

No intervention for patients is planned after the end of the study. However, provisions will be in place for patients still enrolled at the end of the trial to continue to receive study intervention if, in the opinion of the investigator, they are continuing to receive benefit from treatment.

In the event that a roll-over or safety extension study is available at the time of the database closure, patients currently receiving treatment with study intervention may be transitioned to such a study, and the current study would reach its end. Patients in Arm B will still be allowed to cross over to receive acalabrutinib as specified in section 6.7. The roll-over or safety extension study would ensure treatment continuation with visits and assessments per its protocol. Any patient who would be proposed to move to such a study would be asked to sign a new ICF.

Such subjects who are still receiving or will cross over to receive acalabrutinib will continue to be monitored for all AEs up to 30 (+7) days after the last dose of investigational product. For subjects who do continue to receive treatment beyond the closure of the database, investigators will continue to report all SAEs to the sponsor Patient Safety until 30 days after IP is discontinued, in accordance with Section 8.4.1(Reporting of SAEs).

6.8 Crossover

At investigator discretion, subjects randomized to Arm B who have BICR-confirmed disease progression and meet eligibility for crossover may have the option to receive acalabrutinib monotherapy as crossover treatment provided the informed consent of the crossover treatment is signed. After the final analysis and per Amendment 5.0, subjects can cross over with investigator-assessed PD with agreement from medical monitor/study physician prior to the conclusion of the study. Screening assessments for crossover listed in Table 3 should be performed within the screening time window of 42 days (as the EoT/SFU visit or its corresponding tests in terms of schedule may overlap with the crossover screening visit or its corresponding tests, the EoT/SFU visit and its corresponding tests can be waived in such case, e.g. the tests or assessments are scheduled both in EoT/SFU window and crossover screening window. CT scans that showed disease progression from Arm B can be used for the crossover screening CT scan, if within 60 days of crossover dosing Cycle 1 Day 1). Eligibility for crossover includes the following criteria:

- Crossover candidates must have BICR-confirmed or investigator-assessed disease progression.

- ECOG performance status and the laboratory parameters as outlined in the inclusion criteria #4 and #7, and exclusion criteria #8 should be met. See Section 5.1 and Section 5.2.
- There are no concerns by the investigator judgement including but not limited to safety risks, compliance, restrictions and study process requirements.

Crossover candidates may not receive any other anticancer therapy to treat CLL, including acalabrutinib outside the study, from the last dose of Arm B treatment to the initiation of crossover therapy with acalabrutinib. Should a subject develop a second primary malignancy while on trial, crossover option after curative treatment of the second primary malignancy may be considered after discussion with the study physician. Crossover subjects will be treated with acalabrutinib until disease progression based on investigator assessment or unacceptable toxicity. BICR assessment is not required for crossover subjects.

For crossover subjects, AEs will be collected from time of signature of informed consent of crossover treatment throughout the treatment period and including the follow-up period. The follow-up period is defined as 30 days after the last dose of crossover treatment. The other requirements for AE collection and reporting are provided in Section 8.

7 Discontinuation OF TREATMENT AND SUBJECT Withdrawal

7.1 Discontinuation of study treatment

Subjects may be discontinued from IP in the following situations (note that discontinuation from study treatment is NOT the same thing as a complete withdrawal from the study):

- Any subject who has objective evidence of disease progression while receiving protocol required study drug should be discontinued from the study treatment. If there is uncertainty regarding whether there is disease progression, the subject may continue study treatment and remain under disease evaluation until confirmation of disease progression. In particular, transient worsening of disease during temporary interruption of study therapy (e.g., for drug-related toxicity, surgery, or intercurrent illness) may not indicate disease progression. In such circumstances, and if medically appropriate, subjects may resume therapy and relevant clinical, laboratory, and/or radiographic assessments should be done to document whether tumor control can be maintained or whether actual disease progression has occurred.
- Any AE that presents a substantial clinical risk to the subject with continued study treatment dosing.
- Subject decision. The subject is at any time free to discontinue treatment, without prejudice to further treatment.
- Pregnancy in a subject, intend to become pregnant or begin breast feeding.
- Severe non-compliance with the clinical study protocol.
- Start of alternative anti-CLL therapy.
- Study terminated by sponsor.

See the SoA for data to be collected at the time of treatment discontinuation and follow-up and for any further evaluations that need to be completed. Subjects that discontinue study treatment will continue with study follow-up visits until death, withdrawal of consent, lost to follow-up, or study termination, whichever occurs first.

